#### 8.1 Adherence

Data regarding participant's adherence to the study product will be collected from a number of sources:

- Consumption sheet: frequency/amount/quantity of a single glass of milk consumed by the participant will be recorded.
- Product count the trial staff, will undertake regular counts of unused study products.

# 8.2 Acceptability and Compliance

A critical outcome is compliance with the intervention programme. We define compliance as consumption of the allocated milk on >50% of intervention days. This threshold approximates consuming the milk four in every seven days and is based on the implementation of milk fluoridation schemes in schools, where milk is provided only on school days which constitute approximately 53% of a calendar year. We define success with respect to compliance if 75% of the sample meets this criterion. Consumption of assigned milk will be assessed using a consumption sheet collected from the participants.

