# 8. Trial Intervention

The consented care homes will be assigned randomly to one of the study arms: - (a) Group 1: non-supplemented milk (placebo), (b) Group 2: milk supplemented with fluoride (5.0 mg F/l), (c) Group 3: milk supplemented with probiotics (Lactobacillus), and (d) Group 4: milk supplemented with fluoride and probiotics. All subjects will be asked to drink a glass of plain/supplemented milk once daily, five days a week, for nine months. Fluoridated milk or probiotics, or placebo (referred to as the Study product) will be administered by the resident's routine caregiver during medicinal/meal rounds. The study product will be sourced from the manufacturer and transported to the study site. Fluoridated milk will be distributed in a small carton, and the probiotics will be provided as a powder in sealed sachets. The preferred route of administration is as follows:

1. The carton containing fluoridated milk is to be emptied into a tall glass and then consumed.

2. The probiotic powder is to be dispensed in a spoon, then added to a prepared glass of skimmed milk/fluoridated milk, mixed well and then consumed

Each care home will be provided with the manufacturer's dossier detailing the composition of the probiotic form and fluoridated milk. After allocation, probiotic sachets will be distributed to the care home at the beginning of the trial, whereas milk (both skimmed & fluoridated) will be distributed to the trial sites weekly. Participants admitted to the hospital would not be expected to continue taking the study product during their hospital stay.

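### In Groups 3 and 4 compliance is defined on milk that includes the probiotic, but the only measure named for it records a glass of milk and not whether the sachet was added

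*Protocol*

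**What the plan says.** Section 2.4 lists acceptability and compliance first among the primary endpoints. Section 8.2 gives the resident-level criterion, "We define compliance as consumption of the allocated milk on >50% of intervention days", and the sample-level criterion, "We define success with respect to compliance if 75% of the sample meets this criterion". It names one data source: "Consumption of assigned milk will be assessed using a consumption sheet collected from the participants".

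Section 8.1 describes that sheet: "Consumption sheet: frequency/amount/quantity of a single glass of milk consumed by the participant will be recorded". It also lists a second adherence source, under which trial staff "will undertake regular counts of unused study products". Section 8 includes the probiotic in its definition of study product, so this count covers sachets.

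Section 8 describes the product. Fluoride is already in the carton. For Groups 3 and 4, "the probiotics will be provided as a powder in sealed sachets", and "The probiotic powder is to be dispensed in a spoon, then added to a prepared glass of skimmed milk/fluoridated milk". Sachets go to the home once, at the start; milk is delivered weekly.

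Section 11.2 plans the proportion complying with a Clopper-Pearson 95% interval. It does not refer to the product count.

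**The concern.** In Groups 1 and 2 the glass and the study product are the same thing, so a record of glasses drunk is a record of product taken. In Groups 3 and 4 they can come apart at every serving. A Group 3 glass without its sachet is milk without probiotic, and a Group 4 glass without it is what Group 2 receives. A sheet that records only the glass treats these the same as a full serving.

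Hypothesis 1 in section 2.1 concerns milk as a feasible way to deliver both fluoride and probiotics. For two of the four arms the named measure shows that the vehicle was drunk, but not that the probiotic was delivered. Adding the sachet is an extra step for the caregiver, and its feasibility is something this pilot should report. If sachet use is not recorded per resident during the trial, no analysis plan can recover it afterwards.

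**Working it through.** **Inputs.** Total sample 240 (section 11.1). Four arms with equal allocation (section 6.4), so about 60 per arm and 120 in Groups 3 and 4 together; equal arm sizes are an assumption, because homes vary in size. Resident criterion >50% of intervention days and sample criterion 75% (section 8.2). The protocol gives no figure for sachet use, so it is varied over its whole range.

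**The plan's own figure.** The 50% and 75% thresholds are set by definition, so there is no calculation to reproduce. The denominator can be checked. Section 11.1 gives a standardised effect of 0.6 and a 0.05 level with Bonferroni correction. Taking three comparisons, α = 0.05/3 = 0.0167 two-sided. Power is not stated; assume 80%.

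n per arm = 2 × (2.394 + 0.842)² / 0.6² = 2 × 10.47 / 0.36 = 58.2, rounded up to 59. Total 4 × 59 = 236, within 3% of 240.

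**Resident level.** Nine months at five days a week is 9 × (365.25/12)/7 × 5 = 195.7 intervention days. More than half is 98 days (99 if the total is rounded up to 196). A resident in Group 3 or 4 with that many glasses recorded passes on the sheet, whether the sachets used number zero or one per glass.

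**Sample level.** Success needs 0.75 × 240 = 180 residents. Let m be the share of residents in every arm who comply on glasses, and s the share of the glass-compliers in Groups 3 and 4 who also had the sachet on >50% of intervention days.

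- Score from the sheet: m × 240 / 240 = m. It does not depend on s.
- Score on the full product: (120m + 120ms)/240 = m(1 + s)/2.

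| m | Sheet score | 75% rule on sheet | Product score, s = 0 | s = 0.5 | s = 1 |
|---|---|---|---|---|---|
| 75% | 180/240 = 75% | met | 90/240 = 37.5% | 135/240 = 56.3% | 75% |
| 90% | 216/240 = 90% | met | 108/240 = 45% | 162/240 = 67.5% | 90% |
| 100% | 240/240 = 100% | met | 120/240 = 50% | 180/240 = 75% | 100% |

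By the plan's own interval method, 180/240 has limits 69.0% to 80.3%, and 90/240 has limits 31.4% to 44.0%. At m = 75% the plan would report the first pair for every value of s.

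**When the two scores agree on success.** The product score reaches 75% when s ≥ 1.5/m − 1. That is s = 1 at m = 75%, s = 0.67 at m = 90% and s = 0.5 at m = 100%. The closer glass compliance is to the threshold, the less sachet shortfall is needed for the two scores to give different verdicts.

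**The case against.** A reader might infer that the success rule itself passes residents who received no probiotic. The text does not support that. Section 8.2 requires the milk that was allocated, and section 8 defines the Group 3 and 4 allocations as milk with the probiotic in it. A glass without its sachet is not the allocated product, so under the definition that day should not count. This stands: the fault is a mismatch between a sound definition and the measure named for it.

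A reader might also infer that sachets are likely to be missed, or that missed sachets would go unnoticed. Neither is supported. No passage ranks the sachet step below the others. The product is given during medication or meal rounds, section 9 has care home staff trained in delivering it, section 13.1 has trial staff on site two or three times a month looking for deviations, and leftover sachets are counted. What remains is that no rule connects the count to compliance. The protocol does not say whether the count is per resident or per home, and a home-level count cannot classify a resident.

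Two further points are fair. The sheet itself is not shown and may carry a sachet entry; section 8.1 describes none. And a diluted probiotic contrast would mislead no planned efficacy inference, because section 11.1 says the trial is not powered for effects and section 11.2 reports them descriptively. The point therefore rests on the feasibility endpoint alone.

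**Conclusion.** The point holds as a gap between definition and measurement, confined to Groups 3 and 4 (about 120 of 240 residents). The named source describes a glass, the probiotic is a separate sachet, and the one source that could show unused sachets is outside both the >50% and the 75% rule.

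The size can only be stated as a range. With 75% glass compliance in every arm, the stated measure reports success at 180/240, and compliance with the full product is somewhere between 37.5% and 75%. The lower end assumes that no Group 3 or 4 resident meets the criterion on sachets and the upper end that every glass-complier does. The range shows what the measure leaves undetermined and is not a forecast. It also assumes 60 residents per arm and the same glass compliance in each.

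This is worth correcting because compliance is a primary endpoint with a stated success criterion, and the correction is inexpensive if made before data collection.

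**What to change.** 1. Section 8.1: for Groups 3 and 4, add a yes/no entry to the consumption sheet showing whether the sachet was added to that day's glass.
2. Section 8.2: state that in those groups a day counts towards the >50% criterion only if the glass was drunk and the sachet was added.
3. Sections 8.1 and 8.2: in each home, reconcile the recorded glass-plus-sachet days with sachets used according to the count already planned, and report any discrepancy.
4. Section 11.2: report compliance by arm as well as overall, so that a shortfall in the probiotic arms is not hidden in the pooled figure.

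The cost is one more daily entry in two arms and one reconciliation table. The entry is itself a staff report, which is why it should be checked against the count. The reported compliance figure may be lower. No dose, schedule or clinical rule changes.

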# TRIAL SUMMARY

[figure not shown]
| Title                | Improving the oral health of older adults using milk supplemented with fluoride and probiotics: An interventional feasibility study and pilot RCT   |
|----------------------|---|
| Acronym              | ELDER   |
| Short title          | ELDER   |
| Trial configuration  | Multi-centre, open-label, parallel-group, four-arm, prospective, cluster-randomised, placebo-controlled feasibility trial   |
| Trial setting        | Care homes in TeesValley (residential, nursing, mixed)  |
| Planned sample size  | 240 participants  |
| Eligibility criteria | 
 
Care Home (cluster level) criteria:         Inclusions         
 
Site: Tees Valley care homes for older people, with, without nursing or mixed
 
Size: ≥ 5 resident beds in the care home in total with mental capacity
 
 
 
Exclusions
 
 |
|                      | 
 
Care homes not located within the Tees Valley region
 
Care homes with inadequate resident capacity where there are < 5 beds in total
 
   |
|                      | Care Home Resident criteria at trial entry:   |
|                      | 
 
Inclusions
 
Full-time resident in a care home
 
Age ≥ 65 years
 
   |

|  | No acute or immunocompromised medical   |
|--|---|
|  | condition   |
|  | Able to give informed consent for participation   |
|  | Tolerance for dairy products  |
|  |   |
|  | Exclusions  |
|  | Residents who are receiving planned respite or end-   |
|  | of-life or palliative care  |
|  | • Residents who are < 65 years of age   |
|  | Residents with any immunocompromised medical conditions   |
|  | Residents who lack the mental capacity to provide   |
|  | informed consent  |
|  | Residents who are currently taking/being prescribed   |
|  | regular probiotics  |
|  | Residents with severe lactose intolerance   |
|  | Residents who do not have a working level of oral   |
|  | English   |
| Follow-up duration                     | The recruitment window will be open for three months from the official trial start date, and the follow-up schedule will begin from the time the participant gives written informed consent and would from then depend on the length of time the participant remains active in the trial.   |
|  | rengar of time the participant femalis active in the than.  |
|  | Participants will have a baseline assessment and endpoint assessment after nine months.   |

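### Section 8.2 sets the compliance cut-off per undefined intervention day but justifies it per calendar day; on the five-day schedule the two do not match

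*Protocol*

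**What the plan says.** Section 8.2 calls compliance a critical outcome and defines it as "consumption of the allocated milk on >50% of intervention days. This threshold approximates consuming the milk four in every seven days". That equivalence is the first of two reasons given for the figure. The second is an analogy with school milk schemes, "where milk is provided only on school days which constitute approximately 53% of a calendar year". Success is declared if 75% of the sample meets the criterion, which is 180 residents if all 240 planned are counted.

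Section 8 sets the schedule: "All subjects will be asked to drink a glass of plain/supplemented milk once daily, five days a week, for nine months". The Trial Summary (Description of Intervention) also gives five days a week, and caps the period at nine months or 30/12/23, whichever comes first.

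Compliance is part of the first primary endpoint (section 2.4). It is one of the outcomes for which section 11.1 says the study is large enough, and section 11.2 plans an exact confidence interval for the complying proportion. The protocol does not say which days count as intervention days.

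**The concern.** A cut-off and its justification should be on the same scale. Here the cut-off is a share of intervention days, while both justifications are shares of calendar days. With milk on five days in seven the two scales differ by a factor of 7/5, so the same percentage means different amounts of milk.

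At stake is the only outcome for which the protocol gives a numeric success rule. If the denominator is left open, two analysts could classify the same resident differently from the same consumption sheet, and could disagree on whether the 75% target was reached. The exact interval in section 11.2 does not help, because it describes sampling error around a proportion whose defining condition is unsettled.

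**Working it through.** **Inputs**
- Cut-off: more than 50% of intervention days (section 8.2).
- Benchmarks: four in seven days, and 53% of a calendar year (section 8.2).
- Schedule: five days a week for nine months (section 8).
- Assumption: nine months = 39 weeks, so 39 × 7 = 273 calendar days and 39 × 5 = 195 scheduled days. The weekly ratios do not depend on this.

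**Step 1. The stated benchmarks on each scale**
- Four in seven: 4/7 = 57.1% of calendar days; 0.571 × 273 = 156 days; 156/195 = 80% of scheduled days (4 of 5 a week).
- School figure: 0.53 × 7 = 3.71 days a week; 0.53 × 273 = 144.7, so 145 days; 3.71/5 = 74.2% of scheduled days.

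**Step 2. Intervention days = scheduled days**
- More than 0.5 × 5 = more than 2.5 days a week.
- 0.5 × 195 = 97.5, so the rule is met at 98 days; 98/273 = 35.9% of calendar days.
- This does not reproduce 57% or 53%. It asks for (145 − 98)/145 = 32% fewer days than the school figure and (156 − 98)/156 = 37% fewer than four in seven.

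**Step 3. Intervention days = all calendar days**
- More than 0.5 × 7 = more than 3.5 days a week; the smallest whole number is 4 in 7, as section 8.2 says.
- 0.5 × 273 = 136.5, so the rule is met at 137 days; 137/195 = 70.3% of scheduled days.
- The shortfall is small: (145 − 137)/145 = 6% against the school figure and (156 − 137)/156 = 12% against a literal four in seven.
- A resident who drinks every scheduled glass scores only 5/7 = 71.4%.

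**Step 4. What each reading does to a regular weekly pattern**

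| Days drunk per week | Share of scheduled days | Share of calendar days | Compliant, scheduled-day reading | Compliant, calendar-day reading | Meets 53% | Meets 4 in 7 |
|---|---|---|---|---|---|---|
| 2 | 40% | 28.6% | no | no | no | no |
| 3 | 60% | 42.9% | yes | no | no | no |
| 4 | 80% | 57.1% | yes | yes | yes | yes |
| 5 | 100% | 71.4% | yes | yes | yes | yes |

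The readings part company for residents who drink between 98 and 136 of the 195 glasses. The 75% verdict differs when at least 75% of residents reach 98 days but fewer than 75% reach 137. In the limiting case where everyone drinks three days a week, compliance is 100% on one reading and 0% on the other.

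**The case against.** The best defence is that intervention days means every day of the nine-month intervention period. Both justifications are on a calendar-day base, which supports that reading, and step 3 shows that it roughly gives what section 8.2 claims. The school analogy also makes sense as exposure per calendar day. On this reading the three-day-a-week resident fails, and the cut-off is only slightly below its benchmarks.

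This stands far enough to rule out calling the threshold lenient beyond doubt. It does not remove the defect. It counts as intervention days two days in every week on which no milk is scheduled, and it makes full adherence score 71%. Nothing in the protocol tells the analyst to use it, and scheduled days are the more natural meaning given section 8.

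It can also be said that the raw data survive either way: section 8.1 records consumption on sheets and counts unused product, so either denominator can be applied later. That is true, and it makes the repair cheap. But choosing the denominator after the data are seen defeats the purpose of a success rule fixed in advance. Nor is this a detail left for an SAP, since the protocol itself states the cut-off and the rationale that does not fit it.

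**Conclusion.** The point holds. As written, the cut-off and its rationale agree only on a reading that fits the five-day schedule poorly. On the natural scheduled-day reading the cut-off is 98 of 195 days, against 145 and 156 for the benchmarks it is said to approximate; on the calendar-day reading it is 137. These day counts assume 39 weeks; the weekly figures (2.5, 3.5, 3.71 and 4 days) need no assumption.

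Two stronger conclusions might be inferred, and the documents support neither:
- **That the move to a definitive trial hangs on this figure.** Section 8.2 defines success with respect to compliance only, and the protocol states no stop/go rule tied to it.
- **That the declared result will flip.** It can, but only when typical adherence lies between the cut-offs. The protocol gives no expected distribution of consumption, so the likelihood cannot be stated. If most residents drink four or five days a week, or two or fewer, both readings give the same verdict.

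The finding concerns the endpoint definition and takes no view on the milk schedule.

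**What to change.** In section 8.2, define intervention days and state the cut-off and its rationale on that one denominator. Two ways would do:

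1. Express the chosen benchmark as a share of scheduled days: about 74% for the school figure, or 80% for four in seven.
2. Keep more than 50% of scheduled days, delete both justifications, and say plainly that it means more than 2.5 days a week, about 36% of calendar days.

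Whichever is chosen, name it as the one to which the 75% rule applies, and report the compliant proportion at both cut-offs (more than 50% of scheduled days, and the benchmark share) so that readers can see how far the conclusion depends on the choice.

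The cost is a few sentences. The consumption sheets already provide the data, and the sample size is unaffected. The downside is that the compliance figure may look less favourable, either because the bar is higher or because a low bar is now stated openly.

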# 9. Trial Procedure

Care home staff involved in the trial will be trained in trial-specific procedures, including recording participant information and in delivering the study product to the participants. All study appointments will occur at the care home where the participant is a resident.

# 9.1 Data/Sample Collection and Assessment

Eligible participants will have an appointment arranged by their care home staff, at which informed consent will be obtained by the delegated research team member. The following data will be recorded, and samples collected from the trial participants:

- Oral examination: A clinical examination of the oral cavity will include the number of teeth with PRCL. The texture of the lesion will be assessed by visual and tactile examination and will be classified as an 'active' or 'inactive' lesion according to the Petersson and Baysan grading system (29-30). Any signs of gingival inflammation will also be recorded.
- Saliva: Given the age, most of the trial participants will present with a clinical condition called Xerostomia (dry mouth) that might result in their inability to provide an adequate quantity of saliva for microbial testing. Therefore, oral swab samples will be collected by swabbing the buccal mucosa and the anterior floor of the mouth under the tongue. However, from a subset of participants, in addition to an oral swab, whole stimulated saliva will be collected. The latter sample is not mandatory and will only be collected from participants willing to provide this additional specimen.

• Plaque: Supragingival plaque will be collected from a proportion of the teeth diagnosed and graded for PRCL. A sterile interdental brush will be used to scrape plaque from the tooth surface. The collection of supragingival plaque specimens is not mandatory, and a participant deciding not to provide this specimen will still be recruited to the trial.

Those participants with complete tooth loss (edentulous) will only provide saliva samples.

All samples of saliva collected will be cultivated at 37°C for 48h and 96h to measure bacterial and fungal growth. All oral examination, recordings and biological sample collection will be performed by a senior dentist both at baseline and after a subsequent follow-up period of 9 months. A dental hygienist will also be present (not necessarily at all sites) to assist with data collection. The dental examiner, after completing the oral examination, will give these to the trial staff delegated to the respective trial site. The dental assessment will be recorded in a specifically designed record sheet which will be sent to the coordinating centre periodically after completion. All samples/data will be labelled with participant study ID before being sent to the coordinating centre for filling/storage and analysis. Only the research team and laboratory staff at the coordinating centre will have access to trial specimens. The CTC will ensure that the storage, analysis, and disposal of all biological samples will meet the requirements of the Human Tissue Act, 2004. Data collected will be transferred to trial-specific password-protected Excel files with the help of the CTC for subsequent data analysis.

• Medical and dental records: Participants' medical and dental background data will be collected from the care home records and continuously updated during the course of the trial. The dental history collected will include but is not limited to the number of reported episodes of tooth pain, discomfort, sepsis, and unscheduled visits to a dental office. In addition, general medical information such as data on non-scheduled medical episodes, use of pain medication, data on the frequency, recency, and occurrence of bacterial or fungal infections, report of any common bowel problems, domiciliary visits, and hospital admissions will be recorded monthly by the delivery staff into the relevant trial form. The dentist or any member of the research team will collect this information at baseline and then after nine months.

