#### 6.4 Randomisation

The unit of randomisation is the care home (cluster). The care homes will be randomised based on a 1:1 ratio to each available intervention arm or control arm. Trial staff at each trial site will inform the coordinating centre when there are four eligible care homes as they will be randomised in a set of four or six if two sister care homes belonging to the same chain are recruited. As the unit of randomisation is a care home, and the number of participants in each care home is expected to vary, blocking will be used to ensure a close balance of the number of participants (and not necessarily care homes) assigned to each arm. The allocation for a particular trial site will only be revealed after gaining informed consent (i.e., both at the care home level and the individual participant level) and baseline data collection. This approach reduces the threat of post-randomisation selection bias in cluster trials, as individual participants consent to be randomised to one of the four arms rather than being told which arm they have been allocated to if consent is only sought at the level of the care home.

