#### 6.5 Blinding and concealment

As the ELDER trial is an open-label study, the participants, care home staff, and trial team (including the trial statistician and RNs conducting all assessments) will not be blinded to intervention assignment

due to the nature of the trial procedure. However, the dentist performing the baseline and follow-up dental examination will be blinded to intervention and outcome assignment. Release of allocation only following enrolment, resident consent, baseline data collection, and dynamic randomisation of care homes using minimisation will ensure allocation concealment.

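### Section 9.1 lets the blinded examining dentist collect care home record data at nine months: a modest, avoidable risk to blinding

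*Protocol*

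**What the plan says.** Section 6.5 describes an open-label trial with one blinded role. Participants and care home staff know the allocation, and the same section says that the "trial team (including the trial statistician and RNs conducting all assessments) will not be blinded to intervention assignment". The exception is that "the dentist performing the baseline and follow-up dental examination will be blinded to intervention and outcome assignment".

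Section 9.1 says that the oral examinations, recordings and sample collection "will be performed by a senior dentist both at baseline and after a subsequent follow-up period of 9 months". Later in the same section, participants' "medical and dental background data will be collected from the care home records and continuously updated during the course of the trial". The general medical items "will be recorded monthly by the delivery staff into the relevant trial form". The paragraph ends: "The dentist or any member of the research team will collect this information at baseline and then after nine months".

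Section 6.4 makes the care home the unit of randomisation and reveals a home's allocation only after consent and baseline data collection.

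**The concern.** At baseline it does not matter who opens the records, because no allocation has been released. At nine months it does. Everyone in the home who takes or serves the milk knows which product it is, and the home has a single arm. If the dentist learns the arm from one record or one conversation with staff, it is known for every participant in that home.

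What is at stake is the dental grading. Section 9.1 has root caries lesions classed as active or inactive by sight and touch, and gingival inflammation noted at the same examination. These are judgements that knowledge of the arm could colour. They serve objective 1 in section 2.3 and the second primary endpoint in section 2.4. The dentist is the only person the protocol keeps blind, so a task that brings the dentist into the home's records at follow-up needs a reason, and section 9.1 gives none.

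**Working it through.** No figure in the protocol bears on this point, so the check is a comparison of sections.

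1. **Is the dentist in the record-collection sentence the blinded examiner?** Section 9.1 gives the examinations to a senior dentist, and section 6.5 blinds the dentist who does them. The protocol gives no other dentist a part in data collection. The natural reading is that they are the same person.

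2. **Does the task fall after allocation is known?** Yes, for the second collection. Section 6.4 releases allocation after baseline data collection. The baseline collection is therefore harmless, and only the nine-month collection is exposed.

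3. **Is the arm discoverable in the home by then?** Section 6.5 leaves residents and care home staff unblinded. Section 8 describes different presentations: fluoridated milk in cartons and probiotic powder in sachets, stirred into milk by the resident's caregiver. Section 9 places all study appointments in the home.

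4. **Do the records themselves show the arm?** Nothing in the protocol says so. The items listed in section 9.1 are dental complaints and visits, unscheduled medical episodes, pain medication, infections, bowel problems, domiciliary visits and hospital admissions. Two features still matter. Bowel problems could hint at the arm, since section 10.3.2 lists minor gastrointestinal symptoms as reported with probiotics. Infections are a secondary endpoint in section 2.4, so an examiner collecting them is looking at outcome data. Section 6.5 also blinds the dentist to outcome assignment, although that phrase is not explained.

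5. **Does any rule on order or access protect the follow-up grading?** Sections 6.5 and 9.1 state none. They do not require the examination to be completed first, do not mask the records, and do not exclude the dentist from record work.

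6. **Is the dentist needed for the task?** No. The same sentence allows any member of the research team to do it, and delivery staff already record the general medical items each month.

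Steps 1 to 3 and 5 establish a permitted route by which the examiner could learn the arm. Step 4 shows that the route is indirect, and step 6 that it is unnecessary.

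**The case against.** The strongest reply is that the two sections do not conflict. Section 6.5 still binds, and section 9.1 can be followed consistently with it by sending someone else to the records, or by examining everyone in the home first. That is right. A reader might infer that section 9.1 contradicts section 6.5 or that the dentist will be unblinded. The text does not support either, because the wording offers a choice of collector, leaves the order open, and does not place the arm among the items collected. What stands is that the protocol authorises a task which puts its own safeguard at risk, and sets no order or access rule to contain it.

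A reader might also infer that late release of allocation is the protocol's means of blinding the dentist, and that it protects the baseline examination only. Section 6.5 does not say this. It offers "Release of allocation only following enrolment, resident consent, baseline data collection", together with minimisation, as the means of allocation concealment, which is a different matter. Blinding of the dentist is stated as a separate requirement covering both examinations.

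A third reply is that the dentist examines unblinded residents in their own home, so the records are not the only source of exposure and may not be the larger one. This also stands. It limits what the fix can achieve, but an exposure that is hard to remove is no reason to add one that is optional.

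Finally, this is a pilot. Section 11.1 says it is not powered for intervention effects, and section 11.2 presents effects descriptively, without inference about efficacy. That limits the consequence. It does not remove it, because section 11.1 also expects the study to show whether oral health outcomes for a definitive trial can be captured robustly, and an examiner who stays blind is part of that.

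**Conclusion.** The point holds as a minor one. Section 9.1 permits the one blinded assessor to work in care home records at nine months, when the home's arm is known to its staff and residents, with no rule that the examination comes first. The risk is avoidable and not demonstrated.

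Its size cannot be given as a number. The protocol offers no figure for the chance that the dentist learns the arm or for the effect on grading. It would also be wrong to treat every recruited resident's grading as exposed: section 9.1 takes only saliva samples from residents without teeth, and having teeth is not an eligibility condition. What can be said is that any disclosure applies to a whole home, and that the reported arm effects are descriptive.

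The conclusion assumes that the dentist named as a record collector is the examining dentist, and that no separate working instruction already keeps that dentist away from the records. It does not assume that the records show the arm.

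**What to change.** In section 9.1, replace the sentence on who collects the record data with wording such as: *At baseline this information may be collected by the dentist or another member of the research team. At nine months it will be collected by a research team member other than the examining dentist. The examining dentist will not see care home records until the follow-up examinations in that home have been recorded.*

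The cost is one amended sentence and a small shift of work to staff whom section 9.1 already allows to do the task. No new role, visit or form is needed. The change does not deal with what residents or staff may say during the examination; it removes only the exposure that the protocol itself creates.
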